2.4.2. Cardiodynamic Evaluation

A cardiodynamic evaluation of rilzabrutinib was conducted in healthy volunteer subjects in which 400 mg rilzabrutinib, 400 mg rilzabrutinib plus ritonavir, placebo, and moxifloxacin (positive control) were given in separate, randomized periods to healthy volunteer subjects in a 4-way crossover design. Serial ECGs were extracted from continuous Holter monitors at baseline (predose) and for 24 hours post-dose on Day 1 in each period ([Cardiac Safety Report PRN1008-014](#)). Rilzabrutinib at the studied doses did not have a clinically relevant effect on cardiac conduction (ie, the PR and QRS intervals).

In summary, rilzabrutinib at the studied doses did not have a clinically relevant effect on the studied ECG parameters.

2.4.3. Pharmacokinetics and Pharmacodynamics

Rilzabrutinib is rapidly cleared from the plasma, with a terminal half-life of approximately 4 hours, maximum concentration time of approximately 2 hours after ingestion, and a volume of distribution of 149 L after intravenous administration. No significant accumulation was observed after multiple dosing. Approximately 3% of rilzabrutinib is excreted unchanged in the urine.

Rilzabrutinib is available in a tablet formulation for investigation in-patient populations in clinical studies. Food delays the time of observed maximum plasma concentration (T_{max}) by 1.5 hours and decreases AUC and C_{max} of rilzabrutinib by 20% and 30%, respectively, which is not considered to be clinically relevant. Rilzabrutinib showed approximately linear increases in exposure between doses of 150 mg and 600 mg.

Rilzabrutinib demonstrated sustained, dose-dependent occupancy of BTK in peripheral blood mononuclear cells in healthy volunteers. Twice daily dosing with 400 mg tablet is expected to result in BTK occupancy that is within the therapeutic range.

Additional details of the clinical pharmacokinetics (PK) and safety information of rilzabrutinib are provided in the current version of the IB.

2.4.4. Drug-Drug Interaction Potential

Rilzabrutinib is a substrate of the cytochrome P450 (CYP) 3A isoenzyme. In a clinical drug-drug interaction study, the CYP3A inhibitor ritonavir increased plasma rilzabrutinib concentrations (PRN1008-014) and the CYP3A inducer rifampin decreased plasma rilzabrutinib concentration (PRN1008-024); therefore, concomitant use of strong and moderate CYP3A inhibitors or inducers should be avoided. Rilzabrutinib is also a substrate of P-gp from in-vitro studies. However, the P-gp inhibitor quinidine didn't change plasma concentrations of rilzabrutinib (PRN1008-024); thus, rilzabrutinib could be administered with P-gp inhibitors clinically.

In healthy volunteers, 400 mg of rilzabrutinib given simultaneously or two hours prior to the CYP3A substrate midazolam increased the AUC of midazolam by approximately 2-fold, classifying rilzabrutinib as a “weak CYP3A inhibitor” (PRN1008-011). Appropriate caution should be used when co-administering CYP3A “sensitive” substrates with rilzabrutinib, including an assessment of medical risk-benefit for each medication. Consideration should also be given to avoidance of high doses, dose reduction, or replacement of “sensitive” CYP3A substrate drugs. Rilzabrutinib is not an inhibitor of other CYP enzymes. Concomitant administration of rilzabrutinib immediate release (IR) tablet with a proton pump inhibitor, esomeprazole, decreased its exposure by approximately 50%. Concomitant administration of rilzabrutinib IR tablet with famotidine, a histamine 2 (H2) receptor antagonist, modestly reduced (by ~36%) its exposure. When rilzabrutinib IR tablet was dosed at least 2 hours prior to famotidine, no significant exposure change of rilzabrutinib was observed; hence, H2 receptor antagonists should be administered at least 2 hours after rilzabrutinib.

Additional details are provided in the current version of the rilzabrutinib (PRN1008) IB.

2.5. Study Design Rationale

Study PRN1008-018 is a randomized, double-blind, parallel-group, multicenter, placebo-controlled study with a blinded treatment period of up to 24 weeks followed by an open label period of 28 weeks, and a safety follow-up period of 4 weeks, which is intended to evaluate the efficacy and safety of oral rilzabrutinib in participants with refractory or relapsed ITP of >3 months duration in participants aged 18 years and above, and of >6 months duration in pediatric participants aged 12 to <18 years (see [Appendix 10.7](#) for EU [EEA countries], where an age range of 10 to <18 years is applicable). Participants who are eligible at the end of the open label period can be considered for a long-term extension (LTE).

Placebo has been selected as the comparator to rilzabrutinib, as there are no globally approved medicinal products, other than CS (approved in EU but not United States [US]) that could serve as a suitably rapid-acting and active comparator. Use of placebo is ethical in this context, as participants who are on concomitant ITP medications (an oral CS and/or a thrombopoietin receptor agonist [TPO-RA]) will be eligible for the study. Participants have to have an inadequate response to these medications as evidenced by the average of two platelet counts below 30,000/ μ L (with no platelet count greater than 35,000/ μ L) and will have to maintain stable doses of these medications from 14 days before Study Day 1 and until the last dose of study medication. In addition, the use of rescue medications (limited to IVIg, anti-D, CS, and platelet infusion only) will be permitted to increase platelet counts or prevent bleeding when platelet counts are less than 20,000/ μ L, or for bleeding or wet purpura.

The marketed BTK inhibitor, ibrutinib, has been studied in combination with rituximab in the treatment of chronic lymphocytic leukemia without evidence of increased drug-related AEs ([Burger 2017](#)). There is no prior drug interaction potential between anti-CD20 biologic drugs and the small molecule rilzabrutinib.

The primary purpose of the 28-week, open label period is to allow access to study drug for participants who were on placebo medication as well as to evaluate durability of clinical response and accrue additional long-term data on the safety of rilzabrutinib.

The LTE is designed to further evaluate durability of clinical response and accrue additional long-term data on the safety of rilzabrutinib.

During the COVID-19 pandemic, measures to ensure continued drug supply and safety monitoring for participants are described in the “Guidelines to Sites for Delayed Participant Visits or Missed Visits due to travel restrictions and any foreseeable impacts of COVID- 19” ([Appendix 8](#)). These measures include remote study visits, enrollment procedures, direct to participant delivery of study medication and urine pregnancy tests, as well as handling of protocol deviations, and remote site monitoring (where allowed by local regulations).

Enrollment of pediatric participants

Inclusion of participants aged 10 to <18 years in the study is possible based on clinical and pathophysiological similarities between persistent/chronic ITP with adult participants. These similarities include presenting platelet counts (mean, $18.1 \times 10^9/L$ in children and $25.4 \times 10^9/L$ in adults), incidence and type of bleeding when platelet counts are $<20 \times 10^9/L$, family history of thrombocytopenia (2% in children and 3% in adults), rates of treatment (80% of children and 71% of adults at presentation and 58% of children and adults at 6 months, with similarly decreasing rates within both groups at 12 and 24 months) ([Kühne 2001](#), [Schifferli 2018](#)) and similar late remission rates among children and adults with persistent and chronic ITP at 12 and 24 months ([Schifferli 2018](#)). Lowe and Buchanan confirmed that pediatric patients with ITP (age 10 to 18 years) had chronic disease with a chronicity rate up to 57%, which is higher than the rate of chronic ITP in younger children (<10 years of age) ([Lowe 2002](#)). Moreover, it has been reported that children diagnosed with ITP between 10 and 18 years of age showed only a 32% recovery rate ([Lowe 2002](#), [Kühne 2003](#)). The pathological mechanism of ITP (antibody-mediated platelet destruction) as well, is not different between children and adults. It can be expected that rilzabrutinib acts in the same way in adults and children with persistent/chronic ITP. It is well known that the immune system matures and significantly changes throughout childhood ([Blanco 2018](#), [Comans-Bitter 1997](#), [Simon 2015](#)). The most significant changes were observed in the first 10 years of life ([Duchamp 2014](#), [Ghraichy 2020](#), [Piatosa 2010](#)). B-cells percentage declined between the ages of 6 months and 8 years, after which it remained stable at about 70-80%. Memory B-cells are already present at birth and their numbers increase throughout childhood, stabilizing between the ages of 12 and 18 years ([Duchamp 2014](#)). Literature reports indicate that total B-cell counts increase 2-fold immediately after birth, remain high until the age of 2 years, and then gradually decrease approximately 6.5-fold until adulthood ([Blanco 2018](#)). The percentage of naive B-cells among total B-cells decrease steadily from birth to the age of 12 years and the memory B-cell numbers stabilize between the ages of 12 to 18 years ([Duchamp 2014](#)). Total serum IgG levels gradually increase at early ages, and IgG3 and IgG1 levels reach adult like concentrations at 5 to 10 years of age ([Blanco 2018](#)). In addition, renal function and drug metabolizing enzymes are fully developed by age 12 ([Fernandez 2011](#)). Thus, the developmental immunological and physiological characteristics justify the inclusion of children ages 10 to <18 years in the current study.

2.6. Dose Rationale

A dosing regimen of 400 mg rilzabrutinib BID has been selected for evaluation in participants with ITP based on the observed safety and efficacy profile in Study PRN1008-005. In addition, Phase 1 dose-ranging data indicate that the plasma concentrations associated with this dose level are sufficient to maintain near-maximal BTK occupancy over the entire dosing interval, thereby robustly testing the efficacy of BTK inhibition.

Dose-response analyses conducted on preliminary data from Study PRN1008-010 indicate that the 400 mg rilzabrutinib BID dosing regimen was associated with a faster and more pronounced increase in platelet count compared to lower doses. After 28 days of rilzabrutinib treatment, increases in mean platelet count ranged from $7.59 \times 10^9/\text{L}$ at the low dose of 200 mg once daily to $22.5 \times 10^9/\text{L}$ at the high dose of 400 mg BID. In addition, patients treated with lower daily doses were less likely to achieve the primary endpoint (Kuter 2019). Patient responses were improved in patients who started the study at the 400 mg BID dose with 43.8% achieving the primary endpoint of 2 or more consecutive platelet counts, separated by at least 5 days of $\geq 50 \times 10^9/\text{L}$ AND an increase of platelet count of $\geq 20 \times 10^9/\text{L}$ from baseline (Kuter 2020). This evidence of treatment effect supports the evaluation of 400 mg BID in the Phase 3 PRN1008-018 study under this protocol.

The same dosing regimen (400 mg rilzabrutinib BID) has been selected for evaluation in pediatric participants (10 to <18 years of age) as the PK of rilzabrutinib are expected to be similar in pediatric participants (10 to <18 years old) and adults. Rilzabrutinib is metabolized by the CYP3A isoenzyme; the clearance of CYP3A substrates has been observed to be similar in adolescents and adults (Ginsberg 2002), suggesting that the clearance of rilzabrutinib will also be similar in adolescents (12 to <18 years old) and adults, and the adult and adolescent doses were found to be equivalent in the majority of approved drugs in a recent US Food and Drug Administration (FDA) survey (Momper 2013). A body weight ≥ 30 kg is added as inclusion criteria, to ensure the body weight of pediatric participants (10 to <12 years old) is within the 95% percentile body weight of pediatric participants at 12 years old, so that the PK exposure for participants 10 to <12 years is not anticipated to be higher than that for participants at 12 years old, and the same dose (400 mg BID tablet) could be used in the entire pediatric population (10 to <18 years old) (See Appendix 10.7). This dosing regimen is therefore expected to be associated with a comparable benefit-risk profile in adolescent participants with ITP relative to adult participants, and evaluation in this study may expedite the availability of an efficacious treatment to the adolescent population.

Please refer to the IB for more details.

2.7. Overall Risk-Benefit Assessment

2.7.1. Risk assessment

Based on the review of the cumulative data, as of 02 January 2024, with an estimated exposure of 1137 participants who received at least one dose of rilzabrutinib or placebo across multiple disease conditions (826 participants on rilzabrutinib with approximately 545 patient-years, estimated based on randomization ratio), there are no important identified risks for rilzabrutinib. The following are considered as important potential risks for rilzabrutinib:

- Serious infections
- Liver enzyme elevation
- Uveitis

Details of important potential risks together with a summary of the cumulative clinical safety data are provided below.

Table 4 - Risk assessment

Important Potential risk	Summary of data/rationale for risk	Mitigation Strategy
Serious infection	
Rilzabrutinib may increase the risk of serious infection due to inhibition of human B-cell activation and antibody mediated activation of immune cells via FC receptor signaling. Refer to the latest IB for additional detail on the pharmacology of rilzabrutinib.
 
As of 02-Jan-2024, the overall exposure was 1137 participants in Phase 2/3 studies (rilzabrutinib/ placebo) in whom 2 SUSARs of serious infections have been reported in studies of pemphigus (n=1) and ITP (n=1).
 
Most patients have recovered while on treatment with either rilzabrutinib or blinded IMP and cases are confounded by underlying disease and/or treatment with high dose corticosteroids. No imbalance observed between rilzabrutinib arm and the placebo arm for participants treated for Pemphigus (10-May-2022) and CSU (19-Jul-2023). No serious infections were observed in the atopic dermatitis randomized controlled clinical trial (20-Jul-2023). A causal association between IMP and these conditions has not been established.
	
 • Participants with evidence suggestive of active tuberculosis or non-tuberculous mycobacterial infections are excluded. • Participants with a history of serious infection requiring IV therapy within 4 weeks of randomization or with active moderate-to-severe infections at screening are excluded. • Risk management includes screening, regular monitoring, and identification of early signs of infections (HBV, HCV, HIV, or active COVID-19) or with active moderate-to-severe infection. • Routine collection of AEs • Designation of severe or serious infection as an AESI
Liver enzyme elevation	
As of 02-Jan-2024, the overall exposure was 1137 participants in Phase 2/3 (rilzabrutinib/ placebo) studies in whom 26 events of elevations of liver enzymes have been observed in studies with pemphigus, ITP, Asthma, CSU, AD, and IgG4-RD participants. The majority were of mild/moderate severity; few events resulted in interruption of IMP. Most patients had alternative etiologies or confounding factors for the elevations observed. As of 02-Jan-2024, there is insufficient evidence for a causal relationship between liver enzyme elevations and rilzabrutinib. There were no Hy's Law or hepatic failure cases reported.
	
 • Participants with AST/ALT > 1.5 × ULN or total bilirubin >1.5 × ULN are excluded. • Participants with acute or chronic liver disease (other than the disease under investigation) are excluded. • Routine collection of AEs • Routine monitoring of AST, ALT, and total bilirubin • Designation of ALT > 3 × ULN as an AESI and suggested actions and follow up assessments.

Important Potential risk	Summary of data/rationale for risk	Mitigation Strategy
Uveitis	As of 02-Jan-2024, the overall exposure was 1137 participants in Phase 2/3 (rilzabrutinib/ placebo) studies in which cases of uveitis (n=5) occurred, including 2 Vogt-Koyanagi-Harada disease (VKHD) cases. The events of uveitis were observed in different indications across the rilzabrutinib program in studies of pemphigus (n=2), ITP (n=1), and CSU (n=2). All events resolved; 4 of the 5 events resolved with treatment, while continuing rilzabrutinib. A definitive causal association between rilzabrutinib and these ocular conditions has not been established.	
 • Participants are advised to report new onset or worsening eye symptoms to the site study doctor in ICF. • Inclusion of eye-assessment in all physical examinations • Designation of uveitis as an AESI • Examination by an ophthalmologist should be considered for patients who develop ocular symptoms, eg, eye erythema, pain, or blurred vision suggestive of uveitis, as appropriate.

Abbreviations: AE=adverse event; AESI=adverse event of special interest; ALT=alanine aminotransferase; BID=twice daily; BTK=Bruton's tyrosine kinase; CMV=Cytomegalovirus; COVID-19=Coronavirus disease 2019; CSU=chronic spontaneous urticaria; HBV=hepatitis B virus; HCV=hepatitis C virus; HIV=human immunodeficiency virus; IMP=investigational medicinal product; ITP=immune thrombocytopenic purpura; SARS-CoV-2=severe acute respiratory syndrome coronavirus-2; SUSAR=suspected unexpected serious adverse reaction; ULN=upper limit normal.

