- b At the Week 13 visit review previous platelet counts for response during the first 12 weeks. If the participant met the criteria for response continue with the Week 13 visit assessments, the participant should continue in the blinded part. If the participant did not meet the criteria for response, complete the Week 25 visit assessments and the participant may start the open label period or discontinue from the study. Platelet response is defined as a) a platelet count of $\geq 50,000/\mu\text{L}$ OR a platelet count of between $\geq 30,000/\mu\text{L}$ and $< 50,000/\mu\text{L}$ and at least doubled from baseline at any time during the first 12 weeks and b) absence of rescue medication in the 4 weeks prior to the latest elevated platelet count that meets platelet response criteria.) Participants who receive rescue medication during the last 12 weeks also may join the open-label part or discontinue from the study. See [Figure 1](#) for decision tree for assessing response at Week 13 and for calculation of baseline platelet count.
- c For pediatric participants (see [Appendix 10.7](#) for EU [EEA countries] age ranges) height is recorded at Screening, Week 13, Week 25, Week 37, and Week 53. For participants aged 18 years and older height is recorded at Screening only.
- d Full physical examination at Screening, 4-week follow-up and early termination; abbreviated physical examination at all other visits. Medical history should include vaccine history. See [Appendix 10.6](#) for Italy-specific requirements.
- e ECG for pediatric participants (see [Appendix 10.7](#) for EU [EEA countries] age ranges) will be performed predose and 2 hours postdose (± 15 mins) at the Week 1 and Week 25 visits.
- f Urinalysis: pH, specific gravity, protein, glucose, ketones, bilirubin, blood, nitrites, urobilinogen, and leukocytes.
- g Participants enrolled with positive HBV core antibody test result and HBsAb titer ≥ 100 IU/L will have HBV DNA monitored monthly while on treatment and for 6 months after treatment has ended.
- h For women of childbearing potential only. Serum pregnancy test must be performed at Screening; a urine pregnancy test must be performed at all other study timepoints.
- i To confirm postmenopausal status for women who are not surgically sterile and of reproductive potential.
- j Historical lab results may be used for ABO and Rh Blood Type.

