- l QOL Questionnaires include EQ-5D-5L, ITP-PAQ or ITP-KIT, and PGIS-Fatigue/PGIS/PGIC. ITP-PAQ, EQ-5D-5L and PGIS-Fatigue/PGIS/PGIC (in that order) will be administered for adults 18 years or older. ITP-KIT and EQ-5D-5L (in that order) will be administered for pediatric participants (see [Appendix 10.7](#) for EU [EEA countries] age ranges). **Questionnaires should be completed prior to all other study procedures and interactions with site staff.**
- m See [Appendix 10](#) for country-specific requirements.
- n Optional collection of 2 blood samples for vaccine-specific IgG in serum (see [Section 7.9.9](#) for a list of routine vaccines). The first blood sample should be collected within 6 weeks prior to each vaccine dose regimen and the second blood sample should be collected within approximately 3 to 6 weeks after the vaccine dose regimen is complete. Whenever possible, blood for vaccine-specific IgG should be collected at a scheduled visit; but may also be collected during an Unscheduled Visit. Dates of vaccination, disease, brand name of vaccine product and antigenic strain should be recorded.
- o Week 25/SD169 visit is the last visit of the blinded treatment period and may also serve as the start of the open label period.
- p For participants who will enter the open label period directly after 12 weeks of blinded treatment, they will attend the Week 13/SD85 visit which corresponds to the Week 25/SD169 visit (Table 2), this would be their last visit of the blinded treatment period and also the start of the open label period. They will follow the open label period schedule of assessments from Week 29 (Table 2) starting at their next scheduled visit for a total of 28 weeks.
- q For participants who will enter the open label period directly after 12 weeks of blinded treatment, they will follow the open label period schedule of assessments (**Week 25 to Week 53**) which means that they will be treated on the open-label part for a total of 28 weeks. After Week 53, the participants will follow the schedule of assessments according to their eligibility for the LTE period.

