- a Reductions in the doses or withdrawal of concomitant ITP medications will be permitted if the participant achieves platelet count of ≥50,000/μL in three scheduled visits (over 12 weeks). Retreatment with the same medication(s) and doses of ITP concomitant medication(s) used at baseline (an oral CS and/or a TPO-RA), changing the dose or initiation of new ITP medications (an oral CS and/or a TPO-RA) will also be allowed. Tapering of concomitant CS and/or TPO-RA should be performed in accordance with the schedule in Section [6.6.2](#).

- b* Full physical exam at End of Study, abbreviated physical exam at all other visits. See [Appendix 10.6](#) for Italy-specific requirements.
- c* Urinalysis: pH, specific gravity, protein, glucose, ketones, bilirubin, blood, nitrites, urobilinogen, and leukocytes.
- d* Urine pregnancy test for women of childbearing potential only.
- e* Serum chemistry will include the following: aspartate aminotransferase (AST); alanine aminotransferase (ALT); total, direct, and indirect bilirubin levels; alkaline phosphatase (ALP); albumin; creatinine; urea; total protein; sodium; chloride; calcium; phosphate; potassium; and glucose (random).
- f* Hematology will include the following: hemoglobin, hematocrit, erythrocyte count (red blood cell [RBC] count), thrombocyte count (platelets), mean platelet volume, leukocyte count (white blood cell [WBC] count) with differential in absolute counts (including neutrophils, eosinophils, basophils, lymphocytes, and monocytes). Local laboratories will be used for platelet analysis required at ALL visits (ie, Clinic Visits and Unscheduled Lab Visits in between Clinic Visits). The central laboratory will to be used for the analyses required at Clinic Visits including hematology, differential, and reticulocytes. The results of hematology, differential and reticulocytes obtained at local laboratories will be used only if the central lab results of Clinic Visits are missing due to any reason. Central platelet counts assessed at Clinic Visits will be used if local platelet results are missing for any reason. After the end of treatment (EOT) visit, weekly platelet count assessment is not required; however, it is up to the Investigator to decide whether to conduct weekly platelet assessments using unscheduled visits, if deemed necessary for participant safety.

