4.1.4. End of Study visit (Four Weeks Post Last Dose of Study Drug)

The following assessments will be performed four weeks post last dose of study drug in the double blind, open label period, or LTE:

- Complete ITP-PAQ or ITP-KIT, EQ-5D-5L and PGIS-Fatigue/PGIS/PGIC patient questionnaire
- Record concomitant medications
- Record AEs

- Record weight (kg)
- Conduct full physical examination; See [Appendix 10.6](#) for Italy-specific requirements
- Complete IBLS
- Capture vital signs (body temperature, respiratory rate, blood pressure, and pulse rate)
- Collect 12-lead single ECG
- Collect urine sample for urinalysis
- Conduct urine pregnancy test (women of childbearing potential)
- Collect clinical laboratory blood samples:
 - Hematology (hemoglobin, hematocrit, RBCs, platelets, mean platelet volume, WBCs with differentials [neutrophils, eosinophils, basophils, lymphocytes, and monocytes])
 - Serum chemistry (AST, ALT, bilirubin, ALP, albumin, creatinine, urea, total protein, sodium, chloride, calcium, phosphate, potassium, and glucose [random])
 - Coagulation (PT/INR, thrombin time, aPTT, fibrinogen level)
- Collect exploratory laboratory blood samples (see [Appendix 10](#) for country-specific requirements):
 - T/B/NK counts
 - TPO levels
 - Hemolysis panel
 - Immunoglobulin levels
 - (Optional) vaccine-specific IgG response
- For country-specific requirements please refer to [Appendix 10](#).

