7.8.6. Early Termination Visit

Please refer to [Table 1](#) (if terminating during double-blind treatment) and [Table 2](#) (Open-Label Period) for specific ET assessments. An attempt should be made to have the participant return for the ET visit as soon as possible after the last dose of rilzabrutinib or placebo.

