7.9.2. Physical Examination

A full physical examination includes, at a minimum, assessment of the following: skin, eyes, ears, nose, throat, heart, chest/breast, abdomen, neurological system (briefly), lymph nodes, spine, and extremities (skeletal).

An abbreviated physical examination is inclusive of general appearance, cardiac, GI, and pulmonary assessments.

A licensed physician or nurse practitioner (or equivalent) will examine each participant.

Physical examination may be performed at various unscheduled time points if deemed necessary by the Investigator.

See [Appendix 10.6](#) for Italy-specific requirements.

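### The protocol relies on an eye check at every physical examination to mitigate uveitis, but no scheduled examination during dosing includes the eyes

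*Protocol*

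**What the plan says.** Table 4 in Protocol section 2.7.1 gives four mitigations for uveitis. One is "Inclusion of eye-assessment in all physical examinations". The others are consent-form advice to report eye symptoms, designation as an adverse event of special interest, and considering an ophthalmologist's examination when symptoms appear. Section 2.7.3 then concludes that suitable mitigation has been defined for uveitis.

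Section 7.9.2 defines two examinations:

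- Full: "A full physical examination includes, at a minimum, assessment of the following: skin, eyes, ears, nose, throat, heart, chest/breast, abdomen", followed by further body systems.
- Abbreviated: "An abbreviated physical examination is inclusive of general appearance, cardiac, GI, and pulmonary assessments".

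Table 1 footnote d and Table 2 footnote b use the same rule: "Full physical examination at Screening, 4-week follow-up and early termination; abbreviated physical examination at all other visits". For the long-term extension (LTE), Table 3 footnote b says: "Full physical exam at End of Study, abbreviated physical exam at all other visits". The visit lists in sections 4.1.2, 4.1.3 and 4.1.5 agree. They call for an abbreviated examination at Day 1, at every clinic visit from Week 5 to Week 53, and at each LTE visit.

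**The concern.** The risk assessment counts on an eye check at every examination, while the procedure section and the schedules require one only at the full examination. Sites work from the procedure section and the schedules, so a site that follows them exactly can omit the check throughout dosing without deviating from either.

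The safeguard lost is the only scheduled eye check made by an examiner during treatment. The remaining uveitis measures depend mainly on the participant noticing and reporting symptoms. The sponsor classes uveitis as both an important potential risk and an event of special interest. Table 4 reports five cases in the program, two of them Vogt-Koyanagi-Harada disease and one in an ITP study.

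**Working it through.** **Does any required eye assessment fall during dosing?**

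| Examination | Eyes named in 7.9.2? | When scheduled |
|---|---|---|
| Full, screening | Yes | Before the first dose |
| Full, early termination (blinded, open label) | Yes | After the last dose. Section 7.8.6: "An attempt should be made to have the participant return for the ET visit as soon as possible after the last dose" |
| Full, End of Study | Yes | After the last dose. Section 4.1.4: "The following assessments will be performed four weeks post last dose of study drug in the double blind, open label period, or LTE" |
| Abbreviated | No | Day 1, Weeks 5 to 53, all LTE visits before End of Study |

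After screening, every examination that names the eyes follows the last dose.

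**Could other text fill the gap?** Appendix 10.6 (Italy) adds only pediatric Tanner staging to the examination. The bleeding scale in Appendix 1 has a subconjunctival haemorrhage item, but it is taken by history and concerns bleeding only. Section 7.9.2 allows unscheduled examinations at the investigator's discretion and does not define their content. Section 9.1 describes monitoring by abbreviated examinations. The amendment 05 change table records uveitis changes to sections 2.7.1 and 9.3.9.6 but none to 7.9.2, which suggests incomplete carry-through.

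**Clinic visits with no required eye assessment**

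- 24-week pathway: Weeks 1, 5, 9, 13, 17, 21, 25, 29, 33, 37, 41, 45, 49, 53 = 14.
- Week-12 non-responders entering open label: the Week 13 visit serves as Week 25, and then "They will follow the open label period schedule of assessments from Week 29 (Table 2) starting at their next scheduled visit" (Table 2 footnote p). Weeks 1, 5, 9, 13 (4) plus Weeks 29, 33, 37, 41, 45, 49, 53 (7) = 11.
- LTE to Month 12 adds 12 monthly visits: 14 + 12 = 26 and 11 + 12 = 23.
- The Day 1 examination precedes the first dose (section 7.8.2). Leaving it out gives 13, 10, 25 and 22.

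**Interval between required eye assessments, without LTE**

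- End of Study day, 24-week pathway: 365 + 28 = 393, which matches the study day in Table 2.
- End of Study day, Week-12 pathway: 85 + 28 × 7 + 28 = 85 + 196 + 28 = 309.
- With no Day 0, the gap from screening on Day −s to Day D is D + s − 1.

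| Screening day | To Day 393 | To Day 309 |
|---|---|---|
| −1 | 393 | 309 |
| −28 | 420 | 336 |
| −31 (Table 1 footnote a) | 423 | 339 |

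Participants who stop during the blinded or open-label period have shorter gaps, because their early termination visit includes a full examination.

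**The case against.** The strongest reply is that the two texts can be read together. Table 4 is part of the protocol, and the wording of section 7.9.2 does not exclude other body areas from the abbreviated examination. A careful site could therefore add an eye check and satisfy both, and training materials or case report forms, which are not available here, may tell sites to do so. That stands as far as it goes: omission is likely under the text but not proven. Permission is still not a requirement, and naming the eyes for one examination and not the other invites omission.

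The figures can also be read more narrowly. The day counts run from screening to End of Study, so they include time off drug. The dosing interval itself is about 364 days (Day 1 to Day 365) or 280 days (Day 1 to Day 281). In addition, the mitigation came with amendment 05 in May 2024, while the first participant was randomized in April 2021. Only someone enrolled under amendment 05 faces the full run of visits, and the documents do not say how many that is. Both points limit how many participants are affected and for how long, but neither removes the contradiction.

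Finally, the stakes are modest. All five cases resolved, four of them with rilzabrutinib continued, no definitive causal link is established, and a brief inspection will not detect every case of uveitis. This is right, and it sets the weight of the point.

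**Conclusion.** The concern holds. Table 4 commits to an eye assessment at every physical examination, and the operative text requires none between screening and the end of dosing. The shortfall is 14 or 11 clinic visits by pathway (13 or 10 after Day 1), rising to 26 or 23 by LTE Month 12. Without LTE, required eye assessments are 393 to 420 or 309 to 336 days apart, or up to 423 or 339 with the extended screening allowance.

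These figures assume nominal visit days, completion of the stated pathway, and an abbreviated examination limited to the areas that section 7.9.2 names. This is a safety inconsistency that should be corrected. It does not affect the efficacy analysis and is not evidence of harm. Adverse event collection at clinic visits, symptom advice, possible ophthalmology referral, 24-hour reporting of special-interest events and discretionary examinations all continue.

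**What to change.** In section 7.9.2, add a brief inspection of the eyes to the abbreviated examination. The existing schedules then carry it to every clinic visit in Tables 1 to 3. Leave eye symptoms to the open-ended questioning that section 9.3.9.2 prefers, so that adverse event elicitation does not change. Narrowing Table 4 to full examinations would also remove the inconsistency, but only by giving up the check during treatment.

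The cost is one sentence and a minute or two per clinic visit, with no new visit, staff or equipment. It does need a protocol amendment with ethics approval, and health authority approval if substantial, across about 150 sites, so it is best combined with the next amendment.

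As a follow-on, add a uveitis row, including Vogt-Koyanagi-Harada disease, to SAP Table 8 before the later pediatric, open-label and LTE analyses in SAP Table 10. SAP version 3 (18 March 2024) predates amendment 05 (15 May 2024), so this is an update now due and not an error in that version. Uveitis would already appear by preferred term in the cumulative table of all treatment-emergent events.
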